1.0 STUDY SUMMARY

Study Title	A tailored intervention to improve adherence in adolescents and young adults with cancer
Study Design	Randomized feasibility pilot trial
Primary Objective	To conduct a feasibility pilot RCT of a tailored adherence-promotion intervention as compared to uniform standard of care including 40 AYAs with cancer (n = 20 per arm).
Secondary Objective(s)	To explore group differences in improvements in electronically-monitored medication adherence to inform the next phases of intervention development and testing.
Research Intervention(s)/ Investigational Agent(s)	Tailored adherence-promotion intervention
IND/IDE #	Not Applicable
Study Population	Adolescents and Young Adults with Cancer
Sample Size	40
Study Duration for individual participants	Approximately 17 weeks
Study Specific Abbreviations/ Definitions	AYA (Adolescent and Young Adult)

2.0 OBJECTIVES

The purpose of this study is to conduct a pilot feasibility trial of a tailored adherence-promotion intervention as compared to uniform standard of care. This goal will be achieved via the following aims:

Aim 1: Conduct a feasibility pilot RCT of a tailored adherence-promotion intervention as compared to uniform standard of care including 40 AYAs with cancer (n = 20 per arm).

Hypothesis 1a: The intervention will meet enrollment, retention, fidelity, and data completion feasibility criteria.

Hypothesis 1b: AYAs will rate the intervention as easy to use and acceptable.

Exploratory Aim 2: To explore group differences in improvements in electronically-monitored medication adherence to inform the next phases of intervention development and testing.

3.0 BACKGROUND AND SIGNIFICANCE

3.1 Prior Experience and Gaps in Current Knowledge

Clinical care and treatment advances in the last 40 years have increased survival rates by more than 30% for children under 15 with cancer.¹ Progress for adolescents and young adults (AYAs) with the same diagnoses, however, has been far slower, and 5-year survival rates for 20 of the 34 most common AYA cancers have not improved since the 1990s.² Even in diseases where survival rates have improved (e.g., acute lymphoblastic leukemia), AYAs demonstrate particularly poor outcomes and have mortality rates well above those of children < 15 years.³ As a result, cancer remains the leading cause of disease-related death among AYAs ages 15-24 years in high income countries⁴ and accounts for 5% of the AYA lives lost in the United States each year.⁵

A likely contributor to the poor outcomes faced by AYAs with cancer is non-adherence to the oral chemotherapy and/or prophylactic (e.g., antibiotic) medications included in cancer treatment protocols. For patients with leukemia prescribed oral chemotherapy, non-adherence, or medication-taking behavior that deviates from the prescribed treatment protocol,⁶ is associated with a 2.5x greater likelihood of relapse⁷ and a 1.6x greater likelihood of death.⁸ In addition, AYAs with cancer who are non-adherent to antibiotics are 4.6x more likely to die⁹ than adherent AYAs. Our recent systematic review indicated that 21-60% of AYAs with cancer are non-adherent to protocol medications.¹⁰ This means that thousands of AYAs with cancer are currently at risk for devastating consequences which could be prevented.¹¹ In response, professional organizations have endorsed adherence promotion as a standard of pediatric¹² and AYA^{4,13} cancer care.

The factors that may lead AYAs to miss medication doses and thus should be targeted in adherence-promotion efforts can be conceptualized as barriers to adherence. According to the Theoretical Domains Framework, barriers are driven by an individual's capabilities, opportunities, and motivation.^{14,15} Capabilities, opportunities, and motivations change throughout the lifespan and when these domains change, so do our barriers. For example, neurodevelopmental changes beginning at age 15 and stabilizing after age 24 coupled with the developmental transitions of this period (i.e., independent living) mean that AYAs ages 15-24 years display a distinct pattern of capabilities,¹⁶⁻¹⁸ opportunities,¹⁹ and motivation^{16,20,21} and as a result, different barriers to adherence than younger children^{22,23} or older adults.²⁴ Because barriers change with age, improving adherence is likely to require a developmentally-specific approach. While the National Cancer Institute defines the AYA period as 15-39 years,²⁵ a more conservative definition of 15-24 years represents an ideal target population due to the similarities in barriers experienced by AYAs 15-24 years.²⁴

Data from 3 studies²⁶ and 1 systematic review¹⁰ led by [name] (PI), suggest that the capabilities, opportunities, and motivations of AYAs ages 15-24 years with cancer result in 18 primary barriers (Fig 1). One of the challenges to improving adherence is that overcoming each of these barriers requires a distinct set of strategies, or behavior change techniques (BCTs).^{27,28,29} For example, improving adherence in an AYA who forgets her medication (barrier) may require prompts or cues (BCT).³⁰ Alternatively, an AYA who feels his regimen gets in the way of other activities (barrier) may benefit from problem-solving (BCT).³¹ Guided by this theory, we propose that improving adherence requires that each AYA receives BCTs matched to their top barriers.

[figure not shown]

Fig 1. Theoretical Model

Ensuring AYAs with cancer receive BCTs matched to their barriers is not as simple as creating another “one-size-fits-all” intervention. This is because, in our preliminary studies, 81% of AYAs with cancer endorsed different barriers than any other AYA. The vast majority of AYAs, thus, likely need a unique set of BCTs to overcome their barriers and improve their adherence. Guided by these data and theory,^{14,28,31,32} we hypothesize that we can improve on the effects of interventions to date by testing a rigorous tailored adherence-promotion intervention in which each AYA receives BCTs matched to their top barriers. The scientific premise of this approach is supported by an RCT of an adherence-promotion intervention with 4,078 adults with diabetes, hyperlipidemia, and hypertension. Adults who received BCTs tailored to their top barriers exhibited greater improvements in adherence than adults in the control group.³³ Post-hoc analyses of data from the mobile app trial suggest this approach also holds promise for AYA oncology as the 3 of 23 AYAs whose adherence *did* improve were more likely than their peers to endorse forgetting as a barrier.²⁴ The AYAs who improved, thus, happened to receive BCTs (reminders & tracking) targeting their specific barrier.

3.2 Preliminary Data Informing the Proposed Study Design

With support of her NCI K07, [name] is conducting a longitudinal observational study to identify predictors of medication adherence among AYAs (15-24 years) with cancer. Defining adherence as $\geq 95\%$ of prescribed doses taken, the threshold associated with a lower risk of relapse in acute lymphoblastic leukemia,⁷ our preliminary data indicate that 71% of AYAs are non-adherent per electronic monitoring data. This rate of non-adherence may be due to barriers faced by AYAs. At baseline, 90% of AYAs reported ≥ 1 barrier and a greater number of barriers was associated with lower electronically monitored ($r = -.49, p = .01$) and self-reported ($r = -.41, p = .01$) adherence. These data suggest that targeting barriers has the potential to improve adherence. Doing so, however, is complicated by the individual variability inherent in barriers. Of the 54 AYAs reporting barriers, only 10 reported the same barriers. The other 81% reported a different set of barriers than any of their peers. In addition, only 26% endorsed forgetting and/or lack of knowledge, the barriers targeted by previous interventions.^{24,34,35} Because most AYAs have unique barriers, it is not surprising that “one-size-fits-all” interventions targeting barriers endorsed by only some AYAs demonstrate limited efficacy.^{24,34,35} Instead, our data suggest that delivering BCTs tailored to an AYA’s top barriers may improve adherence.

Additionally, with support of her NCI K07, [name] conducted qualitative interviews with 15 AYAs with cancer to understand their intervention preferences. AYAs were enthusiastic about a tailored intervention, with one noting “there are just so many different reasons that somebody might not be receiving their medication.” AYAs, even those living with their parents, reported taking primary responsibility for adherence and wanted a say in if/how their parents or other support person were involved in the intervention. To align with these preferences, the intervention is patient-focused (versus family-based) and AYAs will be invited to engage a parent or other support person to implement BCTs as appropriate (e.g., asking fiancé to remind them to implement the BCT “prompts/cues”). We also matched the tailored adherence-promotion intervention with AYA preferences for “convenient” “every other week” sessions over “a few months” by designing an 8 week intervention that includes 4 bi-weekly videoconferencing sessions, with 4 text check-ins occurring on alternating weeks.

3.3 Scientific and Clinical Significance of the Proposed Study

If feasible and efficacious, this intervention has the potential to transform AYA oncology clinical care across the country. Creating an intervention with standardized modules and a standardized tailoring algorithm means that hospitals could adapt the delivery to fit their institutional resources without compromising “active” components. For example, Hospital A may decide that psychologists are best-suited to deliver all modules of BCTs while Hospital B may have psychologists deliver modules of BCTs for some barriers but engage their social work team to deliver modules of BCTs for others (e.g., cost). The flexibility inherent in this design can facilitate implementation without negatively impacting rigor and allows for adaption to other AYA populations.³⁶

4.0 STUDY ENDPOINTS

4.1 Primary and Secondary Study Endpoints

Hypothesis 1A: The primary endpoint for this study is the enrollment rate. Secondary outcomes for Hypothesis 1A include retention rate, assessment completion, and intervention fidelity as detailed in Table 1.

Table 1. Hypothesis 1A Measures

Domain	Measure	Outcome	Criteria
Feasibility (Hyp 1a)	Enrollment Rate	Percentage of eligible approached AYAs who enroll	≥ 70%
	Retention Rate	Percentage of AYAs completing all study procedures	≥ 80% ³⁶
	Assessment Completion	Percentage of AYAs with complete data	≥ 80% ³⁶
	Intervention Fidelity: Contact ³⁷	Percentage of AYAs who received 4 intervention sessions (planned number of sessions)	≥ 80% ³⁸
	Intervention Fidelity: Length ³⁷	Percentage of AYAs whose average session length was between 30 and 45 minutes (planned session duration)	≥ 80% ³⁸
	Intervention Fidelity: Duration ³⁷	Percentage of AYAs who completed the intervention sessions within an 8-10 week timeframe (8 weeks = planned duration; 10 weeks = upper limit set to include a 2 week buffer to provide flexibility for patients who may be hospitalized and/or experience major complications during the intervention period)	≥ 80% ³⁸
	Intervention Fidelity: Content ³⁷	Percentage of AYAs receiving the BCTs matched to their barriers per protocol (assessed via listening to audio recordings of sessions and coding delivered BCTs using a fidelity rating checklist)	≥ 80% ³⁸

Hypothesis 1B: Outcomes for Hypothesis 1B include usability and acceptability as detailed in Table 2. Open-ended questions regarding usability and acceptability will also be asked to inform potential refinements.

Table 2. Hypothesis 1B Measures

Domain	Measure	Outcome	Criteria
Usability (Hyp 1b)	System Usability Scale (SUS) ³⁹	Mean score of AYAs randomized to treatment group	M ≥ 68 ³⁹
	System Usability Scale Adjective Rating ⁴⁰	Mean score of AYAs randomized to treatment group	M ≥ 4 ⁴⁰
Acceptability (Hyp 1b)	Acceptability & Adherence Scale ⁴¹	Mean score of AYAs randomized to treatment group	M ≥ 28 ⁴²
Refinements	3 Open-Ended Questions (1. What did you like best about the program?; 2. What could we change to make the program better?; 3. Anything else we should think about as we work to make this program better?)		N/A

Exploratory Aim 2: The outcome for Exploratory Aim 2 is electronically-monitored medication adherence.

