5.0 STUDY INTERVENTION/INVESTIGATIONAL AGENT

5.1 Description

The intervention being tested is a tailored adherence-promotion intervention.

Intervention Dose and Duration: AYAs in the intervention group will participate in 4 bi-weekly intervention sessions (1 every other week over 8 weeks). These sessions are estimated to last 30-45 minutes each. On alternating weeks, AYAs will receive a text message check-in from the interventionist. An 8 week duration was selected to mirror the amount of time over which adherence naturally declines, is short enough to be completed during the prescribed oral medication regimen of most AYAs with cancer, and is consistent with the “couple of months” duration preferred by AYAs in our preliminary studies.

Intervention Session Content: During the intervention sessions, each AYA will receive modules of behavior change techniques (BCTs) tailored to their individual barriers. Intervention content (BCTs) will be tailored to each AYA's barriers via a 4-step tailoring process. First, AYAs randomized to the intervention condition will complete a barriers tool. Second, the barriers tool will generate a list of the AYA's top 3 barriers, which will be sent to the interventionist. Third, in the first session, the interventionist will review the list and engage in shared decision-making with the AYA to determine which of the 3 barriers the AYA would like to target. Fourth, following a standardized tailoring algorithm (see Fig 2), the interventionist will select and deliver the module of BCTs matched to this barrier during Sessions 1 and 2. As barriers are likely to change over time, the AYA will complete the barriers tool a second time prior to Session 3 and the AYA and interventionist will again engage in shared decision-making to choose the barrier to be targeted in Sessions 3 and 4.

Figure 2 summarizes the tailoring algorithm and content. When the barrier in column 1 is selected as the intervention target, the interventionist will deliver the BCT(s) in column 2. Each BCT represents a component of a health behavior change intervention that has been standardized via expert consensus and over 10 years of empirical research as published in the Theory and Techniques Tool

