9.0 STUDY TIMELINE

9.1 Subject Participation Duration

Adolescents and young adults enrolled in this study will participate in a 4-week run-in period, 1 week pre-treatment assessment, 8-week intervention or control group, and 4 week post-treatment period. In all, the estimated duration of subject participation is 17 weeks.

Given the demanding nature of cancer treatment, all study procedures can be completed +/- 2 weeks of the planned completion date and still be considered completed "on time."

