13.3 Participant Payment

Participants will be compensated for the time required for assessment completion. Compensation for survey completion (est. completion time: 30-45 minutes) was set at \$20. Participants will be compensated an additional \$5 weekly, for 17 weeks, for using and downloading data from their electronic adherence monitoring device. If a participant completes all Feedback Group or Tailored Group procedures, they will be compensated a \$15 bonus. Participants will also be compensated an additional \$10 upon return of the study-provided electronic adherence monitoring device at the conclusion of the study (either at study completion or at drop-out – whenever the electronic monitoring device is returned).

Table 6. Incentive Schedule

Task	Amount
Pre-Treatment Assessment	\$20
Weekly eCAP downloads (4 week run-in + 1 week for pre-treatment assessment + 8 weeks of intervention + 4 weeks post-intervention = 17 weeks)	\$5/week (total up to \$85)
Group completion bonus	\$15
Post-Treatment Assessment	\$20
eCAP return	\$10
Max Total = \$150	

In the event that a study phone is not returned, we will attempt to reach the family via phone and email and set up a way to retrieve the phone. Given the high costs of the phones, if, after several months it is still not returned, we will offer an incentive of \$50 for the safe return of the working mobile device, no questions asked. Other BMCP faculty have had success in using this procedure to increase mobile device return rates.

All compensation will be managed by the study team at CCHMC and provided via ClinCards.

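### Does the 8-10 week Duration criterion in Table 1 fail participants who finish their four sessions on schedule?

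*Combined protocol and SAP*

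**What the plan says.** Table 1 in section 4.1 splits intervention fidelity into four rows, each with an 80% target. The Duration row is "Percentage of AYAs who completed the intervention sessions within an 8-10 week timeframe". Its gloss reads "8 weeks = planned duration; 10 weeks = upper limit set to include a 2 week buffer", and gives hospital admission or serious complications as the reason for the buffer.

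The programme is described in the same terms elsewhere:

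- Section 3.2: an 8-week intervention of "4 bi-weekly videoconferencing sessions, with 4 text check-ins occurring on alternating weeks".
- Section 5.1: "AYAs in the intervention group will participate in 4 bi-weekly intervention sessions (1 every other week over 8 weeks").
- Section 9.1: "1 week pre-treatment assessment, 8-week intervention or control group, and 4 week post-treatment period".
- Table 6 in section 13.3: "8 weeks of intervention + 4 weeks post-intervention = 17 weeks".

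Section 9.1 adds a general tolerance: "all study procedures can be completed +/- 2 weeks of the planned completion date and still be considered completed" on time. Table 7 in section 17.2 combines the four fidelity components in one row and refers back to the protocol for the meaning of duration.

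No readable part of the plan says when the Duration clock starts, whether it stops at session 4 or at the end of the 8-week programme, or how a finish before 8 weeks is scored.

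**The concern.** The criterion times completion of the sessions, but 8 weeks is the length of the whole programme, including the text check-in weeks. Four sessions two weeks apart have only three gaps, so session 4 falls 6 weeks after session 1. A scorer who took 8-10 weeks as a range with a floor, and counted from session 1, would fail everyone who kept to the schedule and pass only those who ran 2 to 4 weeks late. Fidelity would then be scored back to front.

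The stake is the Duration row of Table 1 and, through it, the combined fidelity row of Table 7. Section 17.2 makes support for Hypothesis 1a depend on the Table 7 criteria. With 20 AYAs in the intervention arm, the 80% mark is 16. In the extreme case that all 20 were exactly on schedule, the closed range on a session-1 clock would pass none of them.

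**Working it through.** **The plan's own figures.** Each session is paired with a text check-in in the alternate week, so the programme is 4 blocks x 2 weeks = 8 weeks. Adding the 2-week buffer gives 8 + 2 = 10 weeks. The study total in Table 6 is 4 + 1 + 8 + 4 = 17 weeks. The 8 and the 10 both reproduce as programme length and programme length plus buffer.

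**Span of the sessions alone.** (4 - 1) intervals x 14 days = 42 days = 6 weeks. The concern has this right.

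**Which weeks hold the sessions.** Section 5.1 says that each text carries the target barrier, and that this barrier is chosen in session 1. A text as described therefore cannot precede session 1, which implies sessions in weeks 1, 3, 5 and 7. Sessions in weeks 2, 4, 6 and 8 are checked as an alternative.

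**Elapsed weeks to an on-schedule session 4:**

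| Clock starts at | Sessions in weeks 1, 3, 5, 7 | Sessions in weeks 2, 4, 6, 8 |
|---|---|---|
| Session 1 | 6 | 6 |
| Start of the 8-week period | 6-7 | 7-8 |
| Start of the pre-treatment week | 7-8 | 8-9 |

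- *8-10 weeks as a closed range:* the three entries of 6 or 6-7 weeks fail, the two of 7-8 weeks reach the floor only at their upper edge, and the entry of 8-9 weeks passes.
- *No later than 10 weeks:* every entry passes, since the largest is 9.
- *Clock at randomization:* section 5.1 says "First, AYAs randomized to the intervention condition will complete a barriers tool" before session 1, so some lag is built in. An on-schedule session 4 reaches 8 weeks on this clock if the lag is at least 8 - 6 = 2 weeks. The plan does not state the lag.

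**Which reading the text supports.**

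1. The Duration cell calls 8 weeks the planned length and 10 weeks the limit. It calls nothing a minimum, and its only reason for flexibility is delay.
2. Section 5.1 itself spreads the four sessions over 8 weeks by counting two-week blocks. Table 1 follows that usage, and counted this way an on-schedule programme lasts 8 weeks.
3. Applying the section 9.1 tolerance to a planned completion at week 8 gives 8 - 2 = 6 to 8 + 2 = 10 weeks. The upper end is Table 1's limit, and the lower end is the 6-week session span.

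**What the unstated clock still affects.** Under the 10-week limit, in the implied layout, an AYA can run late by 10 - 6 = 4 weeks on a session-1 clock, by 10 - 7 = 3 to 4 weeks from the start of the 8-week period, and by 10 - 8 = 2 to 3 weeks from the start of the pre-treatment week. The choice among these clocks matters only for AYAs delayed by about 2 to 4 weeks.

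**The case for a change.** The best case for a change is that the closed range is a natural mistake. The Length row of the same table is two-sided, at 30 to 45 minutes, and a rater could treat Duration in the same way. Section 9.1 does not say that its tolerance governs fidelity scoring. Table 7 only points back to the protocol, so the analysis plan does not settle the matter. The implied layout makes session 1 and the start of the 8-week period the obvious clocks, and those are the ones on which a closed range fails on-schedule AYAs. Fixing the wording in advance would also prevent a choice between readings once results are known.

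Part of this stands: the start event, the end event and the treatment of early finishers are not written down in the text available. The rest carries less weight. The Length row gives two bounds without further comment, whereas the Duration row explains each of its numbers and labels only one as a limit. A closed range would also make the protocol's own schedule a fidelity failure, which any analyst would notice on tabulating the session dates. Finally, Fig 3, which sets out the trial procedures, is not shown in the text available, and section 6.5 leaves delivery and tracking to Standard Operating Procedures that are not included. It is therefore not established that the timing rule is missing from the trial's documents.

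**Conclusion.** The arithmetic behind the concern is correct, but the harm depends on a reading that the Duration cell, section 5.1 and section 9.1 all count against. Read as completion by 10 weeks, with 8 weeks as the planned programme length, the criterion misscores no on-schedule AYA on any clock in the table. The extreme case of none passing out of 20 needs three things together: a floor that the text never states, a clock starting at or close to session 1, and every AYA exactly on time.

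What remains is a gap in detail that analysts can fill sensibly. They would choose a start and end event, report them, and apply the 10-week limit. This assumes that session dates are kept, which is reasonable because every session is recorded (section 6.2.b) and progress is tracked centrally (section 6.5). The choice of clock can move only AYAs with material delay. The measure is secondary and descriptive. The enrollment-rate endpoint, sample size, intervention and data collection are untouched. No change to the plan follows.
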